8.1 Screening

The investigator or subinvestigator will review whether or not prospective subjects meet the inclusion criteria and do not meet the exclusion criteria based on available information and select prospective subjects to whom the explanation for informed consent will be given. Screening is not intended for the final confirmation of eligibility,

but should be performed as accurate as possible to minimize patients found ineligible after informed consent is obtained. The investigator or subinvestigator will prepare a list of patients who receive the explanation for obtaining consent (subject screening list/register).

8.2 Informed consent

The investigator or subinvestigator will provide the explanation for informed consent in accordance with Sections "5.3 Timing and method for receiving informed consent" and "5.4 Points to consider for obtaining informed consent" of the protocol, and obtain written consent from prospective subjects.

8.3 Eligibility Assessment

The investigator or subinvestigator will thoroughly collect information necessary for confirming eligibility and make the final assessment of subject eligibility.

8.3.1 Tests for confirming eligibility

After receiving consent, the tests/observations specified in Section "10.2 Investigation items for eligibility assessment" will be performed.

For the exclusion criteria concerning diseases other than hepatic and renal disorders, subjects without a diagnosis of the diseases or subjects who have not received any therapeutic interventions for the diseases are determined eligible. In addition to the presence or absence of a diagnosis of liver disorder or renal disorder, laboratory values shall be investigated to confirm that the patient does not meet the exclusion criteria.

For patients who are not confirmed to have no organic lesion in the large intestine by colonoscopy or radiographic contrast enema performed within 5 years before provisional enrollment, colonoscopy or radiographic contrast enema shall be carried out for reviewing eligibility to confirm that they do not meet the exclusion criterion. Women of childbearing potential will receive pregnancy test to confirm that they are not pregnant.

The bowel movements status during the 2-week screening period in the patient diary will be checked before enrollment to confirm that applicable exclusion criteria are not met.

[figure not shown]
8.3.2 Eligibility Assessment

The investigator or subinvestigator will closely examine the test/observation results and make the final assessment of eligibility based on whether or not the prospective subject meets the inclusion criteria and does not meet the exclusion criteria.

8.4 Subject enrollment

The investigator or subinvestigator will enter and save enrollment-related information to the Eligibility form of eCRF at the review of laboratory test results of the eligibility test (1) and at the provisional enrollment and

enrollment for each subject who provides his/her consent. An alert will be displayed when the form is not completed or any parameter fails to meet the inclusion criteria or meets the exclusion criteria. The EDC system will select and display the drug number allocated to the subject from the drug numbers allocated to the study site. The investigator or subinvestigator will prescribe the study drug with the allocated drug number and enter the drug number to the subject screening list/register. If allocation is performed for an ineligible patient (with 1 or more alert), the system screen will display that the allocation criteria are not met and the system will not allocate any drug number. In that case, screening failure will be entered in the discontinuation criteria section.

^{*} Patients evaluated as eligible will be enrolled.

8.5 Information to be reported to other departments/hospitals

If any subject is being treated by another physician, the investigator or subinvestigator will inform the physician, under the consent of the subject, of the participation of the subject in the clinical study and of concomitant drugs (therapies) to be restricted during the study.

8.6 Matters to be complied by patients

The investigator or subinvestigator will explain how to take the study drug, examination procedures, and how to handle the patient diary with special attention to the following instructions before prescribing the study drug.

- (1) Subjects will visit the study site on predetermined days to undergo specified tests and examinations.
- (2) Subjects will receive the study drug once daily at approximately 30 minutes before breakfast for 14 days from the next day of the day of enrollment, as instructed by the investigator or subinvestigator.
- (3) Subjects may use the rescue medication when they have no bowel movement for at least 72 hours during the period from the start of the screening period to the last observation/test. Subjects will report the use of the rescue medication to the investigator, subinvestigator, or study collaborator in advance. Subjects may not use the rescue medication in 24 hours before and in 48 hours after the start of the study drug.
- (4) Subjects will enter the following events to the patient diary as they arise.
 Subjects will record the use of laxatives and rescue medication and bowel movement status from the day of the provisional enrollment.
 - (i) Events to be recorded from the provisional enrollment to the day before the start of the screening period
 - Date and time of each bowel movement, stool consistency (Bristol Stool Form Scale), and sensation of incomplete evacuation
 - Date and time of the use of laxatives, Chinese herbal medicines indicated for constipation, supplements, etc. for improving constipation, enema, intestinal lavage, and/or intestinal tract cleaning agents (including commercially available drugs)
 - (ii) Events to be recorded after the start of the screening period
 - Date and time of each bowel movement, stool consistency (Bristol Stool Form Scale), and sensation of incomplete evacuation
 - Date and time of taking the first dose of the study drug
 - Date and time of using the rescue medication
 - Severity of constipation (weekly) and date of evaluation
- (5) That the patient diary should be brought to the hospital at each visit
- (6) Subjects will bring any unused study drugs at Visit 7 or at discontinuation.
- (7) Subjects will bring any unused rescue medication at Visit 5 or 7 or at discontinuation.
- (8) Subjects should not change lifestyle habits such as a dietary life and exercise patterns during the study period.

- (9) Subjects will report the use of drugs including those prescribed at other hospitals or purchased at pharmacies, supplements, and therapies to the investigator, subinvestigator or study collaborator.
- (10) Subjects will comply with the instructions on the prohibited medications/therapies or drugs for which changing the dosage regimens is prohibited, as given by the investigator or subinvestigator.
- (11) Women of childbearing potential will practice contraception using appropriate methods under the instructions of the investigator or subinvestigator during the period from informed consent to the last observation/test.

9. Concomitant Therapies

All used drugs and concomitant therapies will be recorded in the eCRF.

9.1 Prohibited Medications in Concomitant Therapies

9.1.1 Prohibited medications and therapies

The use of the following medications and therapies that may affect this study will be prohibited during the period from the start of the screening period to the last observation/test (for withdrawals, until the completion of observation, tests and investigations performed at discontinuation). However, bisacodyl suppositories 10 mg may be used based on the rules set forth in Section 9.1.2 Restricted concomitant medications (therapies), (1) Rescue medication.

The use of laxatives, Chinese herbal medicines indicated for constipation, supplements, etc. for improving constipation, enema, intestinal lavage, and intestinal tract cleaning agents will be investigated and recorded from 3 days before to the day before the start of the screening period. The use of the following drugs and therapies will be investigated and recorded from the start of the screening period to the last observation/test.

- Different types of laxatives (e.g. magnesium oxide preparations, sodium picosulfate, and sennoside)
- Chinese herbal medicines indicated for constipation (e.g., daio-kanzo-to, choi-joki-to, and dai-saiko-to)
- Drugs for the treatment of irritable bowel syndrome (IBS) (e.g., ramosetron hydrochloride, polycarbophil calcium, and trimebutine maleate)
- 5-HT₃ antiemetics
- Enteric movement accelerating agents (e.g., mosapride citrate, metoclopramide, and domperidone)
- Macrolide antibiotics (e.g., erythromycin, roxithromycin, and azithromycin)
- Antidepressants, antipsychotics, antianxiety agents, and tranquilizers (excluding those used for the treatment of insomnia)
- Anticholinergic drugs (excluding topical agents)
- Nonsteroidal anti-inflammatory drugs (excluding topical agents)
- Supplements, etc. for improving constipation

- Enema and intestinal lavage
- Intestinal tract cleaning agents
- Drugs affecting the amount of bile acid (e.g., colestimide and ursodeoxycholic acid)
- · Other study drugs
- Constipation therapies such as biofeedback
- Digital evacuation

[Rationales for the selection]

These are prohibited because of the potential effect on the efficacy evaluation of AJG533.

9.1.2 Restricted concomitant medications (therapies)

Restricted medications are described below.

(1) Rescue medication

Bisacodyl suppositories 10 mg prescribed for this study may be used under the following conditions.

Bisacodyl suppositories 10 mg may be utilized as a rescue medication only when there is no bowel movement for at least 72 consecutive hours from the start of the screening period to the last observation/test. When there is no bowel movement even after using one dose of bisacodyl suppositories 10 mg, the investigator will determine whether or not the subject can continue the study. When there is no bowel movement for at least 72 consecutive hours after having a bowel movement following the use of the rescue medication, one dose of the rescue medication may be used again.

However, the use of the rescue medication within 24 hours before and 48 hours after the start of the study treatment is prohibited.

The date and time of the use of the rescue medication from the screening period to the last observation/test, if any, will be recorded in the eCRF.

[Rationales for the selection]

Since this is a clinical study of a drug for the treatment of chronic constipation, various types of laxatives are included in the prohibited concomitant medications. Nonetheless, because the screening period is as long as 14 days and this is a placebo-controlled study, the use of the rescue medication is permitted in consideration of the possibility of marked worsening of constipation symptoms during the study. However, the use of the rescue medication within 24 hours before and 48 hours after the start of the treatment is prohibited because it may greatly affect the efficacy evaluation of AJG533.

(2) Drugs of which changes in dosage regimens are prohibited

When any of the following drugs is used at the time of receiving the informed consent and needs to be continued during the study period, the change in its dosage regimen is prohibited during the study period from the time of the informed consent to the last observation/test.

For the drugs of which changing the dosage regimen is prohibited, the name of the drug used from the day of the informed consent to the last observation/test, period of use, and dosage regimen will be investigated and recorded.

- Hypnotics for the treatment of insomnia
- · Calcium antagonists
- Iron preparations

[Rationales for the selection]

The change in the dosage regimen of hypnotics, calcium antagonists, or iron preparations was set because it might affect the efficacy evaluation of AJG533.

9.1.3 Guidance for subjects

Subjects will be instructed to avoid greatly changing their dietary habits and exercise patterns from the start of the screening period to the end of the study (or to the day of the contact specified in "12.2 Discontinuation procedures (4)" if the observations/tests at the discontinuation cannot be performed).

10. Observation, Test and Investigation Items and Schedule

10.1 Outline of observation, test and investigation items and schedule

The observation, test and investigation items in this study are presented in Tables 10-1a and 10-1b. The investigation items and schedule are presented in Table 10-2. The acceptable ranges at each Visit are presented in Table 10-3.

Table 10-1a Observation, test and investigation items related to eligibility confirmation

	Contents
Subject background	Date of birth, inpatient/outpatient status, medical history (including surgical history) *1 and complications *2
Observation/investigation items	Subjective symptoms, objective findings, and use of concomitant medications
Vital signs	Blood pressure (systolic and diastolic blood pressures) and pulse rate
Hematology	White blood cell count, red blood cell count, hemoglobin content, hematocrit, and platelet count
Blood biochemistry	Total protein, albumin, AST (GOT), ALT (GPT), γ-GTP, ALP, LDH, LAP, total bilirubin, urea nitrogen, creatinine, uric acid, LDL-cholesterol, HDL-cholesterol, total cholesterol, triglyceride, CRP, CK (CPK), Na, K, Cl, and Ca
Urinalysis (qualitative)	Glucose, protein, urobilinogen, occult blood, pregnancy test (women only) *3
Items related to bowel movements	Bowel movement status (date and time, stool consistency as measured by Bristol Stool Form Scale) and use of laxatives*4 and rescue medication
Colorectal examination (colonoscopy or radiographic contrast enema)	Colorectal examination will be performed by 8 days before the start of the screening period for subjects for whom the absence of organic disease has not been confirmed with the examination in 5 years before the provisional enrolment.

^{*1:} Medical history: Medically important symptoms or diseases (e.g., those related to the exclusion criteria) that developed within 5 years and cured before the start of the study treatment All laparotomy histories will be recorded.

^{*2:} Complications: Diseases present or symptoms or signs observed at the start of the study treatment and considered as clinically important

^{*3:} Pregnancy test will be performed at Visit 2 only in women of childbearing potential.

^{*4:} Laxatives, Chinese herbal medicines indicated for constipation, supplements, etc. for improving constipation, enema, intestinal lavage, and intestinal tract cleaning agents (including commercially available drugs) used on the day before the start of the screening period will also be investigated.

Table 10-1b Observation, test, and investigation items

	Contents				
Subject background	Gender, birth date, race, medical history (including surgical history)*1, complications*2, and presence or absence of constipation-predominant IBS				
Observation/investigation items	Study drug compliance, use of concomitant medications, subjective symptoms, objective findings, and study completion				
Vital signs	Height, body weight, blood pressure (systolic and diastolic blood pressures), and pulse rate				
Hematology	White blood cell count, red blood cell count, hemoglobin content, hematocrit, and platelet count				
Blood biochemistry	Total protein, albumin, AST (GOT), ALT (GPT), γ-GTP, ALP, LDH, LAP, total bilirubin, urea nitrogen, creatinine, uric acid, LDL-cholesterol*3, HDL-cholesterol*3, total cholesterol, triglyceride, CRP, CK (CPK), Na, K, Cl, and Ca				
Urinalysis (qualitative)	Glucose, protein, urobilinogen and occult blood				
Items related to bowel movements	Bowel movement status (date and time, stool consistency as measured by Bristol Stool Form Scale, and sensation of complete evacuation), constipation severity assessment (date of assessment and severity assessment), and use of the rescue medication				

^{*1:} Medical history: Medically important symptoms or diseases (e.g., those related to the exclusion criteria) that developed within 5 years and cured before the start of the study treatment All laparotomy histories will be recorded.

^{*2:} Complications: Diseases present or symptoms or signs observed at the start of the study treatment and considered as clinically important

^{*3:} LDL-cholesterol and HDL-cholesterol at Visit 7 and at discontinuation will be investigated in a blinded manner.

Table 10-2 Investigation items and schedule

	-				_ Study	per	iod				
		Screening period									
	Informed consent	Eligibility test (1)	Confirmatio n of laboratory test eligibility assessmen	Eligibility test (2) *2	Day of provisional enrollment		Day of enrollment	Starting day of study treatment	Week 1 Visit day		Week 2 Visit day /at disconti- nuation
visit	1	2		3	4		5		6		7
Test/observation time points (day)				to -23	to -16		-1	1	8	14	15
Informed consent	0										
Enrollment and confirmation of eligibility assessment results "			0		0		0				
Medical history ³ , complications ⁴ , presence or absence of constipation-predominant IBS							0				
Clinical examination		0		0	0		0		0		0
TEAEs								- 			\rightarrow
Subject background (gender, birth date, inpatient/outpatient status, and race)		0									
Vital signs (height)							0				
Vital signs (body weight)							0				0
Vital signs (blood pressure, pulse rate)		0					0				0
Colonoscopy or radiographic contrast enema *2				0							
Study drug compliance								<			
Use of rescue medication (patient diary)						<					
Use of laxatives *5 (patient diary)					\longleftrightarrow	Ť					
Use of concomitant medications (patient diary)											\rightarrow
Bowel movement status *6 (patient diary)					←					H	 
Constipation severity evaluation (patient diary)							0		0		0
Hematology		0					0				0
Blood biochemistry (i) (excluding LDL-C and HDL-C)		0					0				0
Blood biochemistry (ii) (LDL-C and HDL-C)		0					0				0
Pregnancy test *7		0									
Urinalysis (qualitative)		0					0				0
Blood collection volume (m_)		7mL					7mL				7mL
Urine collection volume (m_)		10mL					10mL		1		10mL

o: To be performed

- *1: Confirmation of laboratory test eligibility assessment results: Eligibility assessment results will be confirmed for renal and hepatic functions in the eligibility test (1). If eligible, the eligibility test (2) or provisional enrollment will be implemented. If ineligible, the patient will be registered as ineligible.
- *2: Colonoscopy or radiographic contrast enema will be performed by 8 days before the start of the screening period (Day -23) for patients for whom the absence of organic disease has not been confirmed with the examination in 5 years before the provisional enrolment.
- *3: Medical history: Medically important symptoms or diseases that developed within 5 years and cured before the start of the study treatment. However, all laparotomy histories will be recorded.
- *4: Complications: Diseases present or symptoms or signs observed at the start of the study treatment and considered as clinically important
- *5: Laxatives, Chinese herbal medicines indicated for constipation, supplements, etc. for improving constipation, enema, intestinal lavage, and intestinal tract cleaning agents (including commercially available drugs) used from the day of provisional enrollment to the day before the start of the screening period will be recorded.
- *6: The bowel movement status from the day of provisional enrollment will be recorded.
- *7: To be performed only in women of childbearing potential.

Table 10-3 Acceptable range at each visit

Visit	5	6	7 *1
No. of days from the start of study treatment	- 1 day	8 days	15 days
Acceptable range (day)	-1	8 to 10	15 to 17

^{*1:} In principle, the tests at discontinuation will be performed within 2 weeks after the date of the last dose.

Note: Any deviation from these acceptable ranges is considered as a protocol deviation. The acceptable ranges for data adoption are presented in Section "13.3 Data Handling."

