4.3 Exclusion Criteria

Patients who meet any of the following criteria will not be included in the study:

<< At provisional enrollment and enrollment>>

- (i) Patients who have or are suspected to have organic constipation
- (ii) Patients who have or are suspected to have symptomatic or drug-induced constipation
- (iii) Patients who have or are suspected to have slow colon transit type constipation
- (iv) Patients who have or are suspected to have excretory disorder constipation
- (v) Patients with a current or past history of gastrointestinal obstruction
- (vi) Patients with a current or past history of abdominal hernia
- (vii) Patients with a history of laparotomy except simple appendectomy
- (viii) Patients with a history of surgical or endoscopic procedures for cholecystectomy and papillotomy
- (ix) Patients in whom the dosage regimens of medications, of which changing the dosage regimens is prohibited, were changed after the day of informed consent
- (x) Patients who cannot use the rescue medication (bisacodyl suppositories 10 mg)
- (xi) Pregnant, lactating or potentially pregnant women, women who wish to become pregnant from the time of the informed consent to the last observation/test point, or women who do not agree to use appropriate birth control methods (oral contraceptives, intrauterine devices, diaphragm, or compliance with the use of condoms by the partner) (women of childbearing potential will receive pregnancy test to check pregnancy status)
- (xii) Patients with concurrent serious renal disease (creatinine \geq 2.00 mg/dL) or liver disease (total bilirubin \geq 3.0 mg/dL, or AST or ALT \geq 100 U/L)

- (xiii) Patients with concurrent serious heart disease
- (xiv) Patients with malignancies
- (xv) Patients with a history of serious drug allergy
- (xvi) Patients who have participated in a clinical study of AJG533 (who have received AJG533)
- (xvii) Patients who are taking part in another clinical study or patients who took part in another clinical study within 12 weeks before enrollment (providing informed consent) in this study
- (xviii) Patients who are determined by the investigator or subinvestigator to be not suitable for the conduct of the study for any other reasons.

<<At enrollment>>

- (xix) Patients who used the rescue medication (bisacodyl suppositories 10 mg) at least 6 times during the 2-week screening period or patients who used the rescue medication at least 3 times in Week 2 of the screening period

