- (xx) Patients who used the rescue medication for less than 72 hours after defecation during the 2-week screening period
- (xxi) Patients with mushy stool or watery stool (Bristol Stool Form Scale type 6 or 7) in SBM during the 2-week screening period
- (xxii) Patients who used prohibited medications/therapies during the 2-week screening period

[Rationales for the selection]

- (i) to (ix) and (xix) to (xxii): The criteria were set because they might affect the evaluation of the pharmacological efficacy of AJG533.
 - (x) to (xv): The criteria were set to secure patient safety.
 - (xvi): The criterion was set to eliminate the influence of the investigator's or subinvestigator's and patient's preconception caused by the fact that the patient had been treated with AJG533.
 - (xvii): The criterion was set from the ethical perspective and for eliminating the effect on evaluation of AJG533.
 - (xviii): The criterion was set assuming cases for which the investigator or subinvestigator might determine that the patient was not suitable for the study for reasons other than the above criteria from scientific and ethical viewpoints.

5. Patient Informed Consent and Information Provision

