- (18) Type of the IRB investigating and reviewing the appropriateness of the study, matters to be investigated and reviewed by each IRB, and other study-related matters concerning the IRB (including the name and address of the founder of each IRB, accessible information, etc.) and matters concerning written procedures for access by the IRB.
- (19) Mattes to be complied with by subjects
- (20) That data to be checked at enrollment may include data before the informed consent.
- (21) That women of childbearing potential will receive pregnant test before provisional enrollment (eligibility test (1)) to confirm that they are not pregnant
- (22) That women of childbearing potential are expected to practice contraception using appropriate methods (compliance with the use of oral contraceptives, intrauterine devices, diaphragm or condom by the partner, etc.) under the instruction of the investigator or subinvestigator during the period from the informed consent to the last observation/test.

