10.2 Investigation items related to eligibility assessment

The eligibility of patients who provide informed consent will be assessed and eligible patients will be provisionally enrolled by Day -16 before the start of the study treatment. The screening period will be started to assess eligibility based on bowel movements from Days -15 (0:00) to -2 (24:00) in the patient diary. Patients assessed as will be enrolled.

<< Before provisional enrollment>>

(1) Laboratory test (eligibility test (1)): Visit 2

Laboratory tests related to the inclusion and exclusion criteria will be performed.

The following parameters other than those of pregnancy test will be performed at SRL, Inc.

Hematology: White blood cell count, red blood cell count, hemoglobin content, hematocrit,

and platelet count

Blood biochemistry: Total protein, albumin, AST (GOT), ALT (GPT), γ-GTP, ALP, LDH, LAP, total

bilirubin, urea nitrogen, creatinine, uric acid, LDL-cholesterol, HDL-cholesterol,

total cholesterol, triglyceride, CRP, CK (CPK), Na, K, Cl, and Ca

Urinalysis (qualitative): Glucose, protein, urobilinogen and occult blood

Urinalysis (qualitative): Pregnancy test (women of childbearing potential only)

Samples will be collected by SRL Medisearch Inc. or SRL, Inc. and sent to SRL, Inc. Samples will be refrigerated before collection. Measured samples will be stored at SRL Medisearch Inc. until case fixation.

Measurement results will be provided as electronic data to the study site and sponsor and sent as test slips from SRL Medisearch to the study site by mail.

Women of childbearing potential will collect an urine sample at Visit 2, which will be used for the dipstick pregnancy test at the study site.

(2) Colonoscopy or radiographic contrast enema (eligibility test (2)): Visit 3

Colonoscopy or radiographic contrast enema for confirming eligibility will be performed for patients for whom the absence of organic disease has not been confirmed with the examination in 5 years before the provisional enrolment. In that case, colonoscopy or radiographic contrast enema will be performed by 8 days

before the start of the screening period (Day -23) after the eligibility for the other items is confirmed after informed consent.

(3) Other investigation items

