will be documented on its label. The sample will be refrigerated until collection. Only after the administration of the study drug (at Visit 7 or discontinuation), serum will be dispensed in two tubes, and subject ID code and the date of blood collection will be documented on each label. The samples will be refrigerated until collection.

(iii) Blood biochemistry (ii)

LDL-cholesterol and HDL-cholesterol

[Investigation time points: Visits 2, 5, and 7 (or at discontinuation)]

Blood collection for blood biochemistry (i) and (ii) will be performed using one serum separator blood collection tube and processed as follows:

Five mL of whole blood will be drawn in a separately distributed serum separator blood collection tube. Separated serum will be dispensed in a designated container, and subject ID code and date of blood collection will be documented on its label. The sample will be refrigerated until collection. Only after the administration of the study drug (at Visit 7 or discontinuation), serum will be dispensed in two tubes, and subject ID code and the date of blood collection will be documented on each label. The samples will be refrigerated until collection.

The measurements of LDL-cholesterol and HDL-cholesterol after the start of the study drug treatment (at Visit 7 or discontinuation) will be disclosed to those involved in the study including the investigator, subinvestigator, and sponsor after key code breaking.

(iv) Urinalysis (qualitative)

Glucose, protein, urobilinogen and occult blood

[Investigation time points: Visits 2, 5, and 7 (or at discontinuation)]

Ten mL of urine will be collected in a separately distributed poly Spitz tube, and subject ID code and date of collection will be documented on its label. The sample will be refrigerated until collection.

(v) Pregnancy test (women of childbearing potential only)

[Investigation time point: Visit 2]

Urine will be collected and tested using a separately distributed pregnancy test dipstick.

[Rationales for the selection]

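### The only scheduled pregnancy test is at Visit 2, at least 15 days before enrollment and 16 days before first dose, with no maximum age for the result

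*Protocol*

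**What the plan says.** **The criterion.** Exclusion (xi) in Protocol section 4.3 covers pregnancy, possible pregnancy, the wish to become pregnant and refusal of contraception. It adds that "women of childbearing potential will receive pregnancy test to check pregnancy status". It stands under the heading "At provisional enrollment and enrollment", so it has to be true at both steps. For criteria (x) to (xv) the section gives this reason: "The criteria were set to secure patient safety".

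**The test.** Each place that gives a time names one occasion:

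- Table 10-1a, note 3 (section 10.1): "Pregnancy test will be performed at Visit 2 only in women of childbearing potential". The Summary's Table a has the same note.
- Table 10-2 has a single pregnancy-test mark, in the Visit 2 column.
- Section 10.2 places the urine dipstick at Visit 2, read at the study site.
- Section 10.8(1)(v) gives "Investigation time point: Visit 2" and then "Urine will be collected and tested using a separately distributed pregnancy test dipstick".
- Section 5.2, item (21), has the patient told that women of childbearing potential "will receive pregnant test before provisional enrollment (eligibility test (1)) to confirm that they are not pregnant".

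**The calendar.** Section 10.2 says that "eligible patients will be provisionally enrolled by Day -16 before the start of the study treatment". Enrollment (Visit 5) is Day -1, and section 7.1.3 starts dosing the next day. Where a colorectal examination is needed, it takes place by Day -23, after the other eligibility items have been confirmed.

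**The concern.** At Visit 5 the investigator must be satisfied that criterion (xi) is still not met. The only laboratory evidence for this was obtained before the two-week screening period began. Two kinds of pregnancy would escape it: one too early to turn the Visit 2 dipstick positive, and one conceived after Visit 2. The plan schedules no further test before 14 days of dosing. Hematology, biochemistry and qualitative urinalysis are all repeated at Visit 5; the pregnancy test is not.

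What is at stake is the safety of a pregnant subject and fetus, and the soundness of an eligibility check that the protocol itself ties to safety. The sample size and the primary analysis are not affected. The protocol does not contradict itself on the timing. The weakness lies in the timing it chose.

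**Working it through.** **Inputs**

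- Pregnancy test: Visit 2, one occasion (Table 10-2; section 10.8(1)(v)).
- Visit 2 precedes provisional enrollment (section 5.2, item (21)).
- Provisional enrollment: Day -16 at the latest (section 10.2).
- Colorectal examination, when needed: Day -23 at the latest, after the other eligibility items (section 10.2).
- Enrollment: Day -1. First dose: the following day, Day 1 (section 7.1.3; Table 10-3).
- Visit windows: Table 10-3 gives them for Visits 5, 6 and 7 only.

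**Day count.** There is no Day 0, so Day -1 to Day 1 is 1 day. Two of the protocol's own counts fit the day numbering: Day -15 to Day -2 inclusive is (15 - 2) + 1 = 14 days, the stated screening length; Day -23 to Day -15 is 23 - 15 = 8 days, the stated lead time for the examination.

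**Formulas.** For a test on Day -d, the age at enrollment is d - 1 days. The age at first dose is (d - 1) + 1 = d days.

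| Latest possible Visit 2 | Age at enrollment (Day -1) | Age at first dose (Day 1) |
|---|---|---|
| Day -16, no colorectal examination needed | 16 - 1 = 15 days | 15 + 1 = 16 days |
| Day -23, examination needed | 23 - 1 = 22 days | 22 + 1 = 23 days |
| Test repeated on Day -1 | 0 days | 1 day |

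**These are minimums.** They put Visit 2 on the same day as the step that follows it. Note 1 to Table 10-2 requires the Visit 2 renal and hepatic results to be confirmed before that step, and those samples go to a central laboratory. If this takes one day (an assumption), the ages become 16 and 17 days, or 23 and 24 days.

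**No maximum.** The protocol sets no earliest day for Visit 2 and no validity period for the pregnancy result, so the age has no upper limit.

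**No later check by test.** The list of items to be examined before enrollment in section 10.2 covers bowel movements, laxatives, rescue medication and prohibited therapies, but not pregnancy. Section 8.3.1 asks for a pregnancy test without giving a later time.

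**The case against.** The strongest reply is that the single test is a consistent choice with other safeguards around it.

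- **Controls at enrollment.** Visit 5 includes a clinical examination and a second confirmation of eligibility. Under section 8.4 the EDC system shows an alert and withholds a drug number if an exclusion criterion is met. Criterion (xi) is also wider than a test result and can be applied by history. All this is true, but none of it detects an unrecognized pregnancy, and the EDC alert acts only on what is entered.
- **Contraception.** It is required from consent to the last observation, so it covers the gap after Visit 2. It does lower the risk. But the protocol asks for a test as well as contraception, so it does not treat contraception as enough. The accepted methods include condoms and diaphragms.
- **Low hazard.** Section 1 describes the drug as poorly absorbed and reports no embryofetal toxicity at the highest doses examined, 1000 mg/kg/day in rats and 150 mg/kg/day in rabbits. Plasma levels were in the picomole range and below the detection limit 24 hours after 10 mg. This stands and lowers the likely harm. The same protocol still excludes pregnancy on safety grounds.
- **No stated validity period is broken, and age is not risk.** Both points are right. The documents set no limit, and the number of days does not measure how many pregnancies a repeat test would find. A Day -1 dipstick can also miss a very recent conception.
- **Wording.** In the Table 10-1a note, the word for exclusivity most naturally restricts the women tested, not the visits. The finding does not need that sentence: the single mark in Table 10-2 and the single time point in section 10.8(1)(v) carry it.

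**Conclusion.** The concern holds. At enrollment, criterion (xi) rests on a pregnancy result at least 15 days old (22 with a colorectal examination), on contraception and on the investigator's judgment. At first dose the result is at least 16 (or 23) days old, with no stated maximum.

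The day counts follow from the protocol's calendar and assume only that Visit 2 falls on the last permitted day. No number of pregnancies is claimed, because the protocol gives neither the number of women of childbearing potential nor a conception rate. The judgment that a result of this age is too old for a safety criterion is a design view, not a breach of a rule in the document. This is a safety gap that should be closed; it does not touch the efficacy results.

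**What to change.** Add an on-site urine dipstick pregnancy test at Visit 5 (Day -1) for women of childbearing potential. It should be read before the EDC system allocates the drug number, and a positive result entered on the Eligibility form so that allocation is blocked. Keep the Visit 2 test and the contraception requirement, since a Day -1 dipstick can miss a very recent conception.

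The 10 mL urinalysis tube at Visit 5 goes to the central laboratory, so the dipstick should be read at the site from part of the same urine.

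Matching edits are needed in seven places: the notes to Tables a and 10-1a, Tables c and 10-2, section 10.2, section 10.8(1)(v) and consent item (21) in section 5.2. The cost is one more dipstick per woman of childbearing potential plus these edits, including the consent content. No visit or invasive procedure is added.
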